3.4.6 Treatment compliance

Compliance will be assured by supervised administration of the investigational product by the investigator and/or his or her designee.

4. MEASUREMENT OF STUDY VARIABLES

The following study measurements will be obtained. The timing of these measurements is detailed in the study plan (Table 1). The following 'priority order' will be in effect when more than one assessment is required at a particular time point:

- Modified Borg Scale/Bidirectional Dyspnea Index
- Minute ventilation including respiratory rate
- Pulse oximetry
- ABG (will only be performed if a subject experiences an acute episode of dyspnea)
- Spirometry

- Blood pressure/heart rate
- ECG
- PK sample

Note: In order to collect PK sampling at the precise scheduled time, other assessments may be initiated prior to the time point to ensure that the PK sample is collected at the scheduled time. The exact time for PK and PD samples will be recorded in the CRF.

4.1 Medical examination and demographic measurements

4.1.1 Enrollment medical examination and demographic measurements

Each subject will undergo an enrollment medical examination within 21 days before Day 1, Period I. This will consist of the following: (Please refer to Section 4.4 for detailed descriptions of the assessments.)

- A written and approved informed consent form must be signed and dated before screening procedures are performed (the informed consent form must be approved by AstraZeneca and the investigator's Institutional Review Board [IRB])
- Review of inclusion and exclusion criteria
- A standard medical and surgical history and drug history
- Recording of demographic data - date of birth, sex, height, weight, race
- Complete physical examination
- 12-lead ECG
- A blood sample for human immunodeficiency virus (HIV) antibodies, hepatitis B surface antigen (HBsAg), and hepatitis C antibodies (anti-HCV)
- Breath ethanol test
- A fasting blood sample for standard clinical chemistry and hematology assessments, and a mid-stream urine sample for urinalysis and drugs of abuse screen
- Blood pressure and heart rate, height (cm), weight (kg), and oral temperature in °C
- Adverse event and concomitant medication monitoring.

4.1.2 Post-study medical examination

Subjects will return to the study center within 4 to 7 days after Study Day 5 of Period II for the Follow-up visit. At this visit the following procedures and assessments will be performed: (Refer to Section 4.4 for detailed descriptions of the assessments.)

- Complete physical examination
- 12-lead ECG
- Fasting blood sample for standard clinical chemistry and hematology assessments, and a mid-stream urine sample urinalysis
- Blood pressure and heart rate, weight (kg), and oral temperature (°C)
- Adverse event questioning and concomitant medication monitoring

At the completion of the Follow-up visit (Visit 4) procedures and assessments, volunteers may be discharged from the study at the discretion of the investigator.

4.2 Pharmacokinetic measurements

For timing of individual PK samples refer to Table 2 and Table 5.

4.2.1 AZD6140 and AR-C124910XX

4.2.1.1 Determination of drug concentration in biological samples

Samples for measurement of drug concentration of AZD6140 and its metabolite, AR-C124910XX, in plasma will be analysed by York Bioanalytical Solutions, Upper Poppleton, York, UK using fully validated bioanalytical methods. Details of the methods used will be provided in the clinical study report (CSR). Samples will be disposed of after the CSR has been finalized.

4.2.1.2 Collection and processing of biological samples for determination of AZD6140/AR-124910XX in plasma

Venous blood samples (2 mL) for determination of AZD6140 and AR-C124910XX concentrations in plasma will be taken at the times presented in Table 2, Table 3 and Table 5. Blood samples will be collected, labelled and shipped as detailed below. The date and time of collection will be recorded on the appropriate CRF.

Blood will be collected according to site procedure. Disposable needles and disposable and lithium heparinized tubes shall be used. Individual venipunctures for each time point may be performed or an indwelling catheter may be used. Between two consecutive blood samples, the IV cannula of the catheter will be closed using a single-use stylet to avoid the use of saline and from discarding any blood. Blood samples (2 mL) will be collected into a lithium-heparinized tube. The heparin and blood will be carefully mixed. The sample will be placed on ice until centrifugation, which will begin within 30 minutes after the sample is obtained.

The sample will be centrifuged for 10 minutes at 4°C at a relative centrifugal force of 1500g. The resulting plasma will be transferred to a 2.0 mL conical polypropylene tube with screw cap and immediately frozen upright at -20°C or below in a non frost-free freezer and kept frozen at this temperature before, during and after transport to the designated laboratory.

Samples should be stored at -20°C or below and analysed within the timeframe after collection for which the stability in the samples has been validated and found acceptable. Results from analyses stored longer than the period stated will not be reported.

4.2.1.3 Labelling of AZD6140 and/AR-C124910XX plasma samples for shipment to AstraZeneca

The labels supplied by AstraZeneca R & D Wilmington, DE must be applied to the plasma sample tubes. The labels should include the following information for the *scheduled PK samples* in Periods I and II:

Study number: D5130C00028

Subject number:

Tube number:

Period I or II/Study day:

Scheduled time:

Analyte: AZD6140/AR-C124910XX

Matrix: PLASMA

Table 5 Schedule of AZD6140/AR-C124910XX PK blood sampling and tube numbers

Periods I and II			
Study Day	Analyte	Scheduled Time Relative to Dose (Hours)	Tube Number
Day 1	AZD6140/AR-C124910XX	Predose*	1
	AZD6140/AR-C124910XX	2	2
	AZD6140/AR-C124910XX	3	3
	AZD6140/AR-C124910XX	4	4
	AZD6140/AR-C124910XX	8	5
	AZD6140/AR-C124910XX	12*	6
Day 2	AZD6140/AR-C124910XX	0*	7
	AZD6140/AR-C124910XX	3	8
Day 3	AZD6140/AR-C124910XX	0*	9
	AZD6140/AR-C124910XX	3	10
Day 4	AZD6140/AR-C124910XX	0*	11

Periods I and II			
Study Day	Analyte	Scheduled Time Relative to Dose (Hours)	Tube Number
	AZD6140/AR-C124910XX	2	12
	AZD6140/AR-C124910XX	3	13
	AZD6140/AR-C124910XX	4	14
	AZD6140/AR-C124910XX	8	15
	AZD6140/AR-C124910XX	12	16
Day 5	AZD6140/AR-C124910XX	0	17

- Blood sample must be drawn prior to dose administration.

The labels for *unscheduled PK samples* collected during a spontaneous dyspnea episode will include the following information:

Study number: D5130C00028

Subject number:

Period I or II/Study Day:

Collection time:

Analyte: AZD6140/AR-C124910XX

Matrix: PLASMA

4.2.1.4 Shipment of AZD6140/AR-C124910XX plasma samples to AstraZeneca

All PK plasma samples accompanied by the specimen shipment logs will be shipped via an agreed upon overnight courier (World Courier). The frozen samples must be packed securely to avoid breakage during transit, should be double bagged to contain leaks and packed with a sufficient quantity of dry ice to ensure they remain frozen for at least 72 hours to allow for delays in shipment. The samples from each subject will be placed in separate bags and labelled as instructed in Section 4.2.1.2. All applicable shipping regulations must be followed. Documentation sufficient to identify each sample must be included in the shipment.

The primary contact, _____, and the designated laboratory identified below must be notified by e-mail and fax at the time samples are shipped. The fax notification should include a copy of the specimen shipment log.

Samples should only be shipped on Monday through Wednesday. Do not ship on or within two days prior to a legal holiday.

Plasma samples should be shipped to:

Notification to DMPK Sweden:

4.3 Pharmacodynamic measurements

4.3.1 Modified Borg Scale

The modified Borg CR-10 scale will be used to assess the subject's perception of dyspnea at the times pre-specified in the study plan, as well as during the cycle exercise test. Numeric measurement will be recorded on the pCRF and the scale will be kept in the appropriate subject's source document files. (Refer to Appendix E.)

The subject should be given the following instructions:

“This is a scale for rating breathlessness. The number “0” represents no breathlessness. The number 10 represents the strongest or greatest breathlessness you have ever experienced. Prior to completing the minute ventilation test and spirometry tests, you will be asked to point to a number with your finger, which represents your perceived level of breathlessness at that time. Use the written description to the right of the number to help guide your selection. I will say the number out loud in order to confirm your choice. If you have an even stronger or greater intensity of breathlessness than you have ever previously experienced, you should then point to the word “maximal” if the severity is greater than 10.”

The subject should be given the following additional instructions during the cycle exercise test:

“Each minute during the exercise test you will be asked to complete this assessment. During the cycle exercise you may have an even stronger or greater intensity of breathlessness than you have ever previously experienced. You should then point to the word “maximal”, if the severity is greater than 10. You can tell us this number after the mouthpiece has been removed.”

The numeric value the subject reports should be recorded on the pCRF.

4.3.2 Bidirectional Dyspnea Index

The Bidirectional Dyspnea Index is a category scale in which words describing varying degrees of ease or difficulty of breathing are linked to number (+5 to -5). Thus, subjects categorize their sense of breathing effort during study time points as being unchanged (zero), slightly (-1), moderately (-2 to -3), or markedly (-4 to -5) easier; or slightly (+1), moderately (+2 to +3), or markedly (+4 to +5) harder than during the immediately preceding period. (Refer to Appendix F.)

The numeric value the subject reports should be recorded on the pCRF.

4.3.3 Respiratory rate

Respiratory rate should be assessed after the subject has been quietly at rest for at least 10 minutes. Respiratory rate should be assessed by counting the number of breaths for a full minute by direct observation or palpation of the subject's chest wall. A numeric value of the number of breaths per minute as well as the quality of the breaths, (i.e., normal, shallow, labored) should be recorded on the pCRF for each time point observed.

4.3.4 Minute ventilation

The total volume of gas that enters or leaves the lungs each minute is referred to as the minute ventilation. It is the product of tidal volume and respiratory rate. Minute ventilation (VE), tidal volume (V_T), and breathing frequency (f) will be determined with Crapo flowmeter. Volume, barometric pressure, and temperature calibrations will be completed before each test period.

V_E (L/min), V_T (mL/min) and f (b/min) will be recorded on the pCRF for each time point measured.

4.3.5 Spirometry

Spirometry will be performed for asthma and COPD patients at screening to establish entry criteria. Additionally, healthy volunteers will be given the opportunity to attempt spirometry at screening visit to ensure that they can adequately perform the testing during study assessments.

Spirometry will be measured in the seated position using the KoKo testing system. The highest values for forced vital capacity (FVC) and forced expiratory volume in one second (FEV_1) selected from a minimum of three FVC maneuvers will be recorded. Subjects should be allowed time to recover before starting the next test in the series of three; however, the time between tests should not exceed 3 minutes. Predicted values for spirometry were taken from Crapo³.

FVC, FEV_1 and FEV_1/FVC ratio should be recorded on the pCRF.

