2.2 Secondary objective(s)

The secondary objectives of the study are to:

- Assess the effect of AZD6140 on other respiratory parameters;
- Evaluate the pharmacokinetic/pharmacodynamic (PK/PD) relationship between AZD6140/AR-C124910XX concentrations and respiratory parameters in healthy volunteers, mild asthma patients, and mild COPD patients;
- Compare respiratory parameters between the healthy volunteers, mild asthma patients, or COPD patients;
- Compare PK of AZD6140 and AR-C124910XX in healthy volunteers, mild asthma patients, or COPD patients.
- Examine the safety and tolerability of AZD6140 in healthy volunteers compared with mild asthma patients, or mild COPD patients.

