3.3.2 Inclusion criteria

For inclusion in the study subjects must fulfill all of the following criteria:

1. Give written informed consent and agree to comply with all requirements of the study;
2. Generally healthy male or female ages 55 to 75 years, inclusive; within the following 3 cohorts:

Cohort	Volunteer Type	Respiratory criteria
A	Healthy	N/A
B	Mild Asthmatic	Clinical diagnosis > 1 year; FEV ₁ ≥ 70% predicted; no exacerbation in past 8 weeks; reversibility demonstrated within the past year (≥ 12% or 200 mL)
C	Mild COPD	Clinical diagnosis > 1 year; FEV ₁ ≥ 60% predicted; no exacerbation in past 8 weeks; FEV ₁ /FVC ratio < 70%; history of tobacco smoking > 10 pack year

3. Weight at least 50 kg and have a BMI between 18 to 30 kg/m² inclusive unless approved by the sponsor and investigator. (BMI will be calculated as weight in kg/height in m² and will not be reported on the case report form.);
4. Females must be post-menopausal (cessation of regular menses for 12 months) or surgically sterile;
5. Have normal physical examination, laboratory values and vital signs, unless the investigator considers an abnormality to not be clinically significant or a symptom of mild COPD or mild asthma (Cohort B and Cohort C patients);
6. Subjects are able to communicate with the investigator, and to understand and comply with all study requirements.

For inclusion in the genetic component of the study, subjects must fulfill the following criteria:

1. Provision of informed consent for genetic sampling and analyses

If a subject declines to participate in the genetic component of the study, there will be no penalty or loss of benefit to the subject. The subject will not be excluded from other aspects of the study described in this Clinical Study Protocol, so long as they consent.

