3.3.3 Exclusion criteria

Any of the following is regarded as a criterion for exclusion from the study:

1. History of hypersensitivity or adverse reaction to dicalcium phosphate and lactose excipients;

2. Use of prescription medication for a chronic medical condition within 2 months of Day 1 of Period I (Refer to Appendix C: Restricted Medications) unless approved by the investigator and sponsor;
3. Use of prescription medication for an acute medical condition within 4 weeks of Day 1 of Period I unless approved by the investigator and sponsor;
4. Use of aspirin, ibuprofen, or any other drug known to increase the propensity for bleeding within 2 weeks prior to Day 1 of Period I;
5. Use of leukotriene antagonists within 7 days of Day 1, Period I;
6. Use of over-the counter preparations including herbal remedies such as Cordyceps sinensis, dan shen, feverfew, Ganoderma lucidum, ephedra, echinacea, St. John's Wort, and garlic, [aged extract taken on an ongoing basis], ginseng, ginkgo, and vitamin preparations within 7 days of Day 1 of Period I unless approved by the investigator and sponsor;
7. A history or presence of neurological, hematological, psychiatric, gastrointestinal, hepatic, or renal disease, or other condition known to interfere with the absorption, distribution, metabolism or excretion of drugs unless approved by the investigator and sponsor;
8. A personal history of vascular abnormalities including aneurysms; a personal history of severe hemorrhage, hematemesis, melena, hemoptysis, severe epistaxis, or intracranial hemorrhage; rectal bleeding within 3 months prior to screening;
9. History suggestive of peptic ulcer disease or bleeding diatheses;
10. History of diabetes, claudication, CHF (congestive heart failure) or myocardial infarction in the past year;
11. History of anxiety disorder;
12. History of intubation/mechanical ventilation due to respiratory disease or bronchospasms;
- ~~10-13.~~ Platelet count $<100,000/\text{mm}^3$ at screening;
- ~~11-14.~~ A significant history of alcohol or substance abuse within the past year;
- ~~12-15.~~ Surgery or significant trauma within 3 months prior to Day 1 of Period I;
- ~~13-16.~~ Current tobacco use or history of tobacco or nicotine containing products use in the past 6 months;

Formatted: Bullets and Numbering

- ~~14-17.~~ Positive test results for HIV, (human immunodeficiency virus) HBsAg, (hepatitis B surface antigen) or hepatitis C antibody (anti-HCV);

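### Cohort A (healthy) has no pre-specified spirometric limit, so undiagnosed airflow obstruction can enter the reference group, and the two cohort tables disagree on the limits for Cohorts B and C

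*Protocol*

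**What the plan says.** Section 3.3.2 admits "Generally healthy male or female ages 55 to 75 years, inclusive; within the following 3 cohorts". In its cohort table, and again in the table of Section 3.1, the respiratory criterion for Cohort A is N/A.

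For the patient cohorts, Section 3.3.2 requires a clinical diagnosis held for more than 1 year and then:
- Cohort B: FEV1 of at least 70% predicted and "no exacerbation in past 8 weeks; reversibility demonstrated within the past year".
- Cohort C: FEV1 of at least 60% predicted and "no exacerbation in past 8 weeks; FEV ₁ /FVC ratio < 70%; history of tobacco smoking > 10 pack year".

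On the use of spirometry at screening, Section 4.3.5 states: "Spirometry will be performed for asthma and COPD patients at screening to establish entry criteria". For the healthy cohort it states that "healthy volunteers will be given the opportunity to attempt spirometry at screening visit to ensure that they can adequately perform the testing". Footnote g of Table 1 likewise describes the screening assessments as a check that subjects can comply with the procedures.

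The general health requirement is inclusion criterion 5: "Have normal physical examination, laboratory values and vital signs, unless the investigator considers an abnormality to not be clinically significant". Spirometry is not named in it. The tobacco exclusion in Section 3.3.3 reaches back only 6 months.

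**The concern.** Section 3.2 says the asthma and COPD patients are included primarily to learn whether their physiologic response differs from that of healthy volunteers, because dyspnea had been reported in patients but not as a drug effect in healthy volunteers. Section 2.2 makes this an objective: "Compare respiratory parameters between the healthy volunteers, mild asthma patients, or COPD patients". Cohort A is the reference for every such contrast.

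The volunteers are 55 to 75 years old and former smokers are admissible, so some may have airflow obstruction that nobody has diagnosed. Without a spirometric limit for Cohort A, such a person can be counted as healthy. Groups that are meant to differ would then look more alike than they are. Eligibility is set in the protocol, so an analysis plan cannot restore the limit after enrolment.

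**Working it through.** The protocol gives no power calculation or effect size (Section 6.4.4), so there is no figure of its own to reproduce. The check has four steps.

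**1. Can an obstructed subject qualify for Cohort A?** Take a hypothetical volunteer in the age range with 15 pack-years, tobacco stopped 12 months ago, FEV1 75% predicted, FEV1/FVC 66%, no respiratory diagnosis, no restricted medication and an unremarkable physical examination.

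| Rule | Result |
|---|---|
| Cohort A respiratory criterion (3.1, 3.3.2) | None to fail |
| Inclusion 5: examination, laboratory values, vital signs | Met; spirometry is not part of it |
| Exclusion 7: organ disease | Not triggered |
| Exclusion 12: past intubation or ventilation | Not triggered |
| Exclusion 16: tobacco within 6 months | Not triggered |
| Exclusion 24: investigator judgment | Discretionary; no threshold stated |

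Against the Cohort C row, the same subject meets the FEV1 limit (75% against at least 60%), the ratio limit (66% against below 70%) and the smoking criterion (15 against more than 10 pack-years). With no exacerbation in 8 weeks, only the clinical diagnosis of more than 1 year is missing.

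**2. Effect on the expected contrast.** Let m of the n subjects in Cohort A be of this kind, each responding a fraction k of the way from the healthy mean to the COPD mean (0 ≤ k ≤ 1). The expected healthy-versus-COPD contrast is multiplied by 1 − k·m/n.
- n = 8, m = 1, k = 1: 1 − 1/8 = 0.875, a loss of 12.5%.
- n = 8, m = 2, k = 1: 1 − 2/8 = 0.75, a loss of 25%.
- n = 8, m = 1, k = 0.5 (assumption): 1 − 0.5/8 = 0.9375, a loss of 6.25%.
- n = 12 (the maximum randomized per cohort), m = 1, k = 1: 1 − 1/12 = 0.917, a loss of 8.3%.

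For comparison, the standard error of a difference between two cohorts of 8 is SD × √(2/8) = 0.5 SD. If the true contrast were 1 SD (assumption), one subject with k = 1 would move it by 0.125 SD, a quarter of one standard error.

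**3. How likely is it?** The protocol gives no rate. If a proportion p of those who pass the existing screening had unrecognised obstruction, the chance of at least one in 8 is 1 − (1 − p)^8.

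| p (assumed) | At least one of 8 | At least two of 8 |
|---|---|---|
| 5% | 34% | 6% |
| 10% | 57% | 19% |
| 20% | 83% | 50% |

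**4. The two cohort tables side by side.**

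| Item | Section 3.1 | Section 3.3.2 |
|---|---|---|
| Cohort A | N/A | N/A |
| Cohort B FEV1 | > 70% | ≥ 70% predicted |
| Cohort C FEV1/FVC | Not stated | < 70% |
| Diagnosis > 1 year (B, C) | Not stated | Stated |

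A Cohort B candidate at exactly 70% predicted is eligible under Section 3.3.2 and not under Section 3.1. A Cohort C candidate with a ratio of 70% or more fails Section 3.3.2 but meets no ratio test in Section 3.1.

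**The case against.** The best counter-argument is that Cohort A is already screened. Criterion 5 requires a normal examination, and its allowance for signs of mild asthma or COPD is confined to Cohorts B and C. The complete examination includes the lungs (Section 4.4.11.1). Medical and medication histories are taken, chronic prescription drugs are restricted, and exclusion 24 leaves room for judgment. This stands for known lung disease. It does not close the gap for obstruction that is undiagnosed, or that is waived as not clinically significant.

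It is also fair that cohort comparison is a secondary objective, that no formal analysis is planned (Section 6.4.3), and that pre-dose spirometry is collected in every subject (Table 2), with respiratory data listed individually (Section 6.4.3.1). A misfit could be seen afterwards, though no rule says what to do about it.

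A reader might infer more than the documents support:
- **That the exclusion list overlooks lung disease.** The list that begins "A history or presence of neurological, hematological, psychiatric, gastrointestinal, hepatic, or renal disease" applies to all cohorts. Naming respiratory disease there would exclude Cohorts B and C.
- **That the screening result is discarded.** Section 4.3.5 has FVC, FEV1 and their ratio recorded, and an investigator could act on them. What is missing is a threshold.
- **That Cohorts B and C are freely interchangeable.** Their measured limits overlap, but each also needs its own clinical diagnosis of more than 1 year. Misplacement would take a dual or wrong diagnosis.
- **That the safety review of Cohort A before Cohorts B and C is weakened.** The documents do not show this. An obstructed subject would, if anything, make a respiratory signal more likely to appear.

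**Conclusion.** The point holds in limited form. No spirometric limit is pre-specified for the healthy cohort, and a subject below the protocol's own FEV1/FVC limit for COPD can enter it if undiagnosed. The loss in the expected healthy-versus-COPD contrast is at most 12.5% per such subject among 8. That bound assumes a response lying between the healthy and COPD means and is reached only at the COPD mean. The chances of 34% to 83% of having at least one such subject follow from assumed rates of 5% to 20%; they are not estimates for this trial and take no account of how well the existing screening works.

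Only secondary, descriptive contrasts are affected. Respiratory rate and minute ventilation on AZD6140 against placebo are compared within subject, and a cohort label does not bias that comparison. The disagreement between the two cohort tables is a separate, plain inconsistency that affects subjects at or near the limits.

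**What to change.** - In the cohort tables of Sections 3.1 and 3.3.2, replace N/A for Cohort A with: no history of asthma, COPD or other chronic lung disease, and a screening FEV1/FVC not below 70%.
- In Section 4.3.5, make screening spirometry required for Cohort A and state that the result decides eligibility. Add it to the screening procedures in Section 4.1.1, which do not list it.
- Reconcile Sections 3.1 and 3.3.2 on the Cohort B FEV1 limit, on the Cohort C FEV1/FVC criterion and on the required duration of diagnosis, preferably by keeping one table and referring to it.

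The cost is eligibility wording and a few more screen failures in Cohort A. The test is already marked at screening in Table 1, so no new procedure is needed.
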